1.1 Synopsis

Title:	University of Michigan Mechanistic Research Center (BACPAC Study)
Grant Number:	1U19AR076734-01
Study Description:	A long-term pragmatic trial in a cohort of patients with chronic low back pain (cLBP). Using a sequential, multiple assignment, randomized trial (SMART) study design. This will consist of a 4-week run-in period using an online cognitive-behavioral self-management intervention (PainGuide), followed by two 8-week treatment periods. Participants between the ages of 25–70 years old who have cLBP and who are eligible will be followed for approximately nine months. Those who have had minimal or modest improvement in their pain (PGIC≥2) after the PainGuide run-in period will be randomized to one of the four 8-week long interventions. These interventions are Mindfulness-Based Stress Reduction (MBSR), physical therapy (PT) and exercise, acupressure self-management, or duloxetine. After that first 8-week treatment, participants with minimal or modest improvement in their pain (PGIC≥2) will be randomized to a second treatment (one of the three treatments not received before). A subset of participants will complete an additional deep phenotyping assessment.
Objectives*:	
Primary Objective: To perform an Interventional Response Phenotyping study in a cohort of cLBP patients.
 
Secondary Objectives:
 
1. To demonstrate that currently available, clinically-derived measures, can predict differential responsiveness to the above therapies2. To identify new experimental measures that predict differential responsiveness to each of the above therapies, as well as to infer mechanisms of action of these treatments.
Endpoints*:	
1. Primary Endpoint: Pain Change in PROMIS Pain Interference between T2 and T3 study visits2. Secondary Endpoints:
a. Change in the Pain, Enjoyment and General Activity (PEG) Scale between T2 and T3 study visits.b. Change in Patient Global Impression of Change (PGIC) between T2 and T3 study visits
Study Population:	Participants between the ages of 25–70 years old who have cLBP
Description of Sites/Facilities Enrolling Participants:	This study will recruit from 6 outpatient clinics catering to low back pain patients at the Michigan Medicine. There will be no sites outside of the US.
Description of Study Intervention/Experimental Manipulation:	There will be 4 study interventions that participants maybe randomized to in this study. They are: 
1. Mindfulness Based Stress Reduction (MBSR): 9 sessions over 8 weeks delivered virtually and in a group setting.2. Physical Therapy (PT) plus exercise: 10 sessions over 8 weeks delivered individually.3. Acupressure: self-administered, daily over 8 weeks.4. Medication- Duloxetine: self-administered medication, daily over 8 weeks.
Study Duration*:	41 months
Participant Duration:	9 months

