8.1 Criteria for randomization

Randomization will occur at T2 and T3 study visits. Participants with minimal or modest improvement in pain after the PainGuide run-in (PGIC \geq 2) will be randomized. Participants who have a robust improvement in their pain (PGIC<2) will not be randomized to treatment. These non-randomized participants will still complete the remaining study visits and mini-assessments. In order to assign equal numbers of participants to each of the 4 study interventions, randomization probabilities will account for the fact that certain participants, e.g. because of a contraindication, may be eligible for only 3 of the 4 treatments.

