## 4.3 Endpoints

The primary study endpoint is the change in the PROMIS (Patient-Reported Outcomes Measurement Information System) pain interference score between the T2 pre-intervention visit and T3 post-intervention visit. The PROMIS pain interference measures the degree to which a patient's pain interferes with the patient's life. The survey questions assess interference in different domains including work around the home, recreational activities, and social activities. A univariate pain interference score is calculated from the respondent's answers. This process is described in Section 9.2.

The study's secondary endpoints consist of the change in the Pain Intensity (PEG) and the Patient Global Impression of Change (PGIC) between the T2 pre-intervention visit and T3 post-intervention visit. The other exploratory PROMIS measures will include a measure of physical functioning, fatigue, sleep disturbances, and cognition. The process of computing each secondary endpoint from survey responses is found in Section 9.2.

Figure 1 Study aims and overview

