## 6 Sample Size

The study aims to continue randomizing patients with cLBP to initial treatment until 102 randomized patients per group are available for the analysis (i.e. completed their T1-T4 visits and had PGIC $\geq$ 2 at T2). This is the target patient group. Based on assumed attrition rates we expect the total number of consented patients to be over 500. Attrition rates include patients who are not randomized because their pain was “very much improved” after run-in (PGIC=1 at T2). Such patients will still be included in the analysis with their limited data. The power analysis, however, excludes these patients because effects in the randomized participants are of primary interest. The smaller subgroup based on 40 patients will be from the target patient group for deep phenotyping for specific treatments.

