### 6.1 Power for explaining treatment effects

Consider a regression model for correlating within-patient improvement (primary: change in PROMIS Pain Interference; secondary: change in PEG, PGIC; many others as exploratory, see below for details) due to one of the 4 main treatments with a phenotypic variable. Using a two-sided test for correlation at 5% significance level we conclude that we will have the power of at least 80% to detect correlations of 0.28 or higher, conservatively assuming the model is applied to one randomized treatment segment with 102 patients. This corresponds to first phase or second phase treatment in one of the 4 treatment groups, and a model based on the light phenotyping target patient group of 408 total. Similar analysis for the smaller subgroup based on 40 patients with available deep phenotyping for a specific treatment and segment shows that correlation of 0.42 or higher will be detectable with 80% power. This is well within reach as evidenced by available literature on the association between treatment effects and phenotype variables. For example, mindfulness and pain responses showed correlations of 0.43-0.51 in prior reported studies. Our previous studies of the association between pain centralization and analgesic responses in knee osteoarthritis showed similar or higher correlations.

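### The secondary endpoint 'change in PGIC from T2 to T3' subtracts a run-in response rating, not a baseline state; define it as the T3 PGIC rating with T2 PGIC as a covariate

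*Protocol*

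**What the plan says.** Protocol 1.1 (Endpoints) names as the second of two secondary endpoints "Change in Patient Global Impression of Change (PGIC) between T2 and T3 study visits". SAP 4.3 says that the "secondary endpoints consist of the change in the Pain Intensity (PEG) and the Patient Global Impression of Change (PGIC) between the T2 pre-intervention visit" and the T3 visit. SAP 6.1 lists the outcomes whose correlation with a phenotype is powered, and includes "secondary: change in PEG, PGIC".

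The documents also show what PGIC does at each visit:

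- **T2.** Protocol 8.1 bases the first randomisation on it: "Participants with minimal or modest improvement in pain after the PainGuide run-in" (PGIC of 2 or more) are randomised. SAP 6 describes those not randomised as very much improved "after run-in (PGIC=1 at T2"), so 1 is the best score and lower is better.
- **T3.** The undifferenced rating decides re-randomisation. Protocol 1.1: "After that first 8-week treatment, participants with minimal or modest improvement in their pain" (again PGIC of 2 or more) go on to a second treatment.
- **T1.** The schedule in SAP Table 1 has no PGIC mark at T1. The first falls at T2.

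SAP 4.3 refers the reader to Section 9.2 for how each secondary endpoint is computed, but 9.2 contains no scoring rule. SAP 8.2 says only that instruments are scored as their authors recommend. No section gives the recall period of the PGIC question or a rule for differencing it.

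**The concern.** PROMIS Pain Interference and PEG measure a state, so subtracting the T2 value gives movement over the treatment period. PGIC measures movement already. Its T2 value records how the patient rated the run-in, so T3 minus T2 mixes response to PainGuide into a quantity that is labelled response to MBSR, PT, acupressure or duloxetine.

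The trial exists to find phenotypes that predict response to each treatment. On a raw PGIC difference, a phenotype that predicts only the run-in rating would tend to show up as a predictor of response to the randomised treatment, with its sign reversed. A phenotype that predicts only the T3 rating could be diluted. The named endpoint also disagrees with the way the trial itself uses PGIC, which is undifferenced at both T2 and T3.

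**Working it through.** **1. The plan's own figure.** SAP 6.1 states at least 80% power for a correlation of 0.28 with n = 102, two-sided 5%. By Fisher's z, power = Φ(atanh(r)·√(n−3) − 1.96) = Φ(0.2877 × 9.950 − 1.96) = Φ(0.902) = 81.7%. A simulation of the t test gives 82.0%. The figure reproduces.

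**2. Range of the difference.** The best T3 score is 1. A randomised patient rated 2 at T2 can gain at most 2 − 1 = 1 point; one rated 4 can gain 3. The possible gain is fixed by the run-in rating, whatever the recall period.

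**3. What a difference means under each recall period.** The documents define only 1. A 7-point scale with 4 = no change is assumed here.

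| T2, T3 | T3 − T2 | If each rating covers the preceding period | If both ratings refer to enrolment |
|---|---|---|---|
| 3, 3 | 0 | improved equally in both periods, scored as no response | no movement since T2 |
| 6, 4 | −2 | worse in run-in, unchanged on treatment, scored as response | real recovery since T2 |
| 2, 3 | +1 | still improving, scored as worsening | lost ground since T2 |

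Under the enrolment reading a steady improver could go from 3 to 2 and score −1, as intended.

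**4. Effect on a correlation of the kind powered in SAP 6.1.** Assume equal SDs and a T2–T3 correlation ρ, which the documents do not give. Take a phenotype that correlates 0.28 with the T3 rating and 0 with the T2 rating.

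- Correlation with the raw difference: 0.28/√(2(1−ρ)).
- Partial correlation with T3 adjusted for T2: 0.28/√(1−ρ²).
- Correlation of the difference with the T2 rating: −√((1−ρ)/2).

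Power uses the formula in step 1 with n = 102.

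| ρ | r, raw difference | Power | r, T3 adjusted for T2 | Power | Difference vs T2 rating |
|---|---|---|---|---|---|
| 0 | 0.198 | 51.5% | 0.280 | 81.7% | −0.71 |
| 0.2 | 0.221 | 61.0% | 0.286 | 83.3% | −0.63 |
| 0.3 | 0.237 | 67.0% | 0.294 | 85.3% | −0.59 |
| 0.5 | 0.280 | 81.7% | 0.323 | 91.6% | −0.50 |
| 0.7 | 0.361 | 96.5% | 0.392 | 98.5% | −0.39 |

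T3 alone gives 81.7% in every row. By symmetry, a phenotype that correlates 0.28 with the T2 rating and 0 with T3 would be flagged on the raw difference at the rates in the third column, with reversed sign. A phenotype that correlates equally with both ratings would cancel.

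**5. The planned models.** SAP 9.1.1 regresses Y₃ on terms that include Y₂. SAP 9.1 repeats the analysis for PGIC, so Y₂ becomes T2 PGIC. If E[Y₃] = Xβ + cY₂, then E[Y₃ − Y₂] = Xβ + (c − 1)Y₂, so every coefficient except that of Y₂ is unchanged. In one simulated data set of 408 patients the treatment-by-phenotype coefficient was −0.602 (robust SE 0.126) for both outcomes, while the Y₂ coefficient moved from 0.303 to −0.697. Only leaving Y₂ out changed the interaction, to −0.753 (SE 0.138). SAP 9.2 also includes the baseline outcome and penalises only the additional predictors, so the same algebra applies.

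**The case against.** The strongest reply is that the planned inference never forms the subtraction. This stands: by step 5, the stage 1 interaction estimates in SAP 9.1.1 and 9.2 are the same either way. SAP 6.1 is a sample-size justification rather than the analysis model. A reader might infer that the planned tests for PGIC are biased by run-in response because of the subtraction; the documents do not support that.

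The second reply concerns the recall period. A reader might infer that steady improvers necessarily score zero and that run-in worseners necessarily appear to respond. Both results need a T3 question that asks about the treatment period. Some uses point that way: PGIC is also given at PT weeks 4 and 8 (Protocol 9.2, Table 3) and at 4 and 8 weeks after a non-study intervention (Protocol 11). But SAP Table 1 also marks it at T5 and at mini-assessments, where no treatment has just ended. The text of the item is not given, so these examples can only be conditional. The limit in step 2 does not depend on the recall period.

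Third, a reader might take the last column of step 4, squared, to mean that 25% to 50% of the endpoint's variance is run-in response. That formula holds for any change score with equal SDs, including the primary endpoint, and it rests on assumed values. If the T2 SD were 0.8 of the T3 SD, which the entry cut-off at 2 makes plausible, the correlation at ρ = 0.5 would be (0.4 − 0.64)/(0.8 × √0.84) = −0.33, or 11% of variance. No such share should be quoted as a finding.

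Finally, the SAP 4.3 sentence can be read so that the word change governs PEG only. Protocol 1.1 does not allow that reading.

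**Conclusion.** The point holds in limited form. As worded in Protocol 1.1, the endpoint is a difference between two ratings of change, and the subtracted one grades the run-in. This affects the endpoint as defined and reported, unadjusted change-score summaries and correlations (SAP 8 plans correlations of phenotypes with responses), and the outcome named in SAP 6.1. It does not affect the primary endpoint or the stage 1 interaction estimates of the planned models.

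The size is known only under assumptions. With equal SDs and a phenotype related only to the T3 rating, power on the raw difference is 51.5% to 67.0% for ρ of 0 to 0.3, equals that of T3 alone at ρ = 0.5, and exceeds it above that. T3 adjusted for T2 does better than the raw difference at every ρ examined. Whether individual scores mislead as in step 3 cannot be settled until the recall period is stated.

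**What to change.** - In Protocol 1.1 and SAP 4.3 and 6.1, define the secondary endpoint as the PGIC rating at T3 (lower is better), with T2 PGIC as a covariate and not subtracted. This agrees with SAP 9.1.1 and works under either recall period.
- Analyse it as ordinal with the proportional-odds model that Protocol 18.1.5 already plans for ordinal responses, and say so in SAP 9.1, which at present repeats the linear model. The algebra in step 5 is specific to a linear mean model, so under proportional odds the outcome has to be named explicitly.
- State the recall period of the existing PGIC item at each visit, and correct the SAP 4.3 cross-reference on scoring. Do not re-word the item: it belongs to the HEAL minimum data set and it decides re-randomisation.

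The cost is an amendment to the endpoint wording in both documents and wherever the endpoint is registered. No new data are needed.

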1.2 Schema

R= Randomization

EMA= Pro-diary wrist device

MBSR=Mindfulness based stress reduction

*=completed remotely online

Figure 1 BACPAC Study Diagram of Study Visits

1.3 Schedule of Activities

Table 1 BACPAC Study- Schedule of Activities and Associated Events

Neurotesting-Achilles Deep Tendon Reflex	x				b			b						
Neurotesting-Sensation	x				b			b						
Neurotesting-Ankle Dorsiflexion (L4)	x				b			b						
Neurotesting-Great toe extension (L5)	x				b			b						
Neurotesting-Hamstrings (S1/S2)	x				b			b						
Neurotesting- Single Leg Calf Raises (S1/S2)	x				b			b						
Neural Tension- Passive Straight Leg Raise + Tightness	x				b			b						
Cross Straight Leg Raise	x				b			b						
SI Provocation- Compression	x				b			b						
SI Provocation- FABER Test	x				b			b						
Fortin Test	x													
Neurotesting-Hip flexion (L2/L3)					b			b						
Neurotesting- Quadriceps (L3/L4)					b			b						
Neurotesting-Seated Slump Test with Active Straight Leg Raise (ASLR)					b			b						
Neurotesting- Brighton Score (Pinky, Thumb & Elbow)					b			b						
Neurotesting- Brighton Score (Knees & Hands to floor)					b			b						

Hip Abduction-Dynamometer					b			b								
SI Provocation-Distraction					b			b								
SI Provocation-Thigh Thrust					b			b								
SI Provocation-Gaenslen's					b			b								
SI Joint- Active Straight Leg Raise					b			b								
SI Provocation-Sacral Thrust					b			b								
Hip Extension Dynamometer					b			b								
Lumbar Segmental Mobility (PA Spring Test)					b			b								
Prone Instability Test					b			b								
Inclinometer-Flexibility- Flexion, Extension and Side bending					b			b								
Observation for Aberrant Motion					b			b								
Directional Preference- Repeat flexion, extension, side glide					b			b								
Hip Provocation-FADDIR					b			b								
Pain Provocation-Quadrant Test					b			b								
Pheno Device- Motion Assessments & Spine Kinematics Data	x															
Biospecimen Collection																
Whole blood	x															
Blood Serum																
RNA PAXgene																

Saliva															
Urine Pregnancy Test	x		x	x		x	x		x	x					x
Imaging- MRI of Back and Pelvis	x														
Questionnaire Data															
Pain Duration and Frequency (cLBP)- 2 Items from NIH Research Task Force Minimum Dataset*		x			x			x						x	
Pain location- Radicular Pain Questions Adapted from NIH Research Task Force Minimum Dataset*		x			x			x					x		
Pain Somatization- Abbreviated Pain Somatization Adapted from NIH Research Task Force Minimum Dataset*		x			x			x					x		
Low Back Pain- Specific Pain Intensity*	x		x	x		x	x		x			x	x	x	x
Opioid use- Single- Item Current Opioid Use*	x		x	x		x	x		x			x		x	
Pain Intensity (PEG)*	x			x			x		x			x		x	
PROMIS Physical Functioning 6b*	x		x	x		x	x		x			x	x	x	x
PROMIS Anxiety 4a*	x		x	x		x	x		x			x	x	x	x
PROMIS Depression-4	x		x	x		x	x		x			x	x	x	x
PROMIS Fatigue	x		x	x		x	x		x			x	x	x	x
PROMIS Sleep Disturbance 6a*	x		x	x		x	x		x			x	x	x	x
Sleep Duration*	x		x	x		x	x		x			x	x	x	x
PROMIS Social Role Activity	x		x			x			x			x	x	x	x

PROMIS Pain Interference 4a*	x	x		x	x			x	x			x			x	x	x	x	x	x
PROMIS Cognitive Function		x		x	x			x	x			x			x	x	x	x		
PROMIS Pain intensity	x		x	x			x	x			x			x	x	x	x	x	x	
Pain Catastrophizing Scale (PCS)*	x		x	x			x	x			x			x		x				
Patient Health Questionnaire-2 (PHQ-2)*		x			x			x								x				
Generalized Anxiety Disorder-2 (GAD-2)*	x			x				x								x				
Patient global impression of change (PGIC)/Global Rating of change (GROC)*			x	x		b	x	x		b	x			x		x	x	x	x	
Tobacco, Alcohol, Prescription medication, and other Substance use (TAPS)*	x			x				x								x				
Fibromyalgia (FM) Survey Criteria 2016 (Widespread Pain Index (WPI) and Symptom Severity Index (SSI))		x		x			x				x			x	x		x			
Widespread Pain*	x			x				x								x				
Life Orientation Test-Revised (LOT-R)	x		x					x				x			x					
Chronic Overlapping Pain Conditions Screener (COPCS)	x			x				x												
Pain Self-efficacy Questionnaire (PSEQ)	x		x				x				x			x						
PainDETECT	x		x	x		x	x	x			x			x		x				
Oswestry Disability Scale (ODI)	x		x			b	x			b	x			x						

Chronic Pain Acceptance Questionnaire (CPAQ-8)	x		x			c	x			c	x		x			
Fear Avoidance Beliefs Questionnaire (FABQ+Physical Activity)	x		x				x			x			x	x		
Experiences Questionnaire (EQ)-11	x		x				x			x			x	x		
Experiences Questionnaire (EQ)-5						c				c						
Perceived Stress Scale (PSS)	x		x				x			x			x			
Positive and Negative Affect Scale (PANAS)	x		x				x			x			x			
Childhood and Recent Traumatic Events Scale (CTES)	x															
Credibility and Expectancy Questionnaire (CEQ)			x				x			x			x			
Client Satisfaction Questionnaire (CSQ)	x		x				x			x			x			
HEAL Treatment Expectancy v1.0 Short Form 6a	x		x				x			x			x			
Numeric Pain Rating Scale (NPRS)	x	x		x	x	b		x	x	b		x	x			
General Sensory Sensitivity (GSS-8)	x		x	x			x	x			x		x	x	x	
Ecological Momentary Activity (EMA) Mental and Physical Symptoms			x			x			x			x	x			
Low-Back Pain Treatment Categories Questionnaire	x		x				x			x			x	x		

Patient Preference Questionnaire		x															
Patient Outcome Questionnaire		x															
BACPAC Customer Service Questionnaire						x							x				
Randomization			a			A											
Adverse Event Reporting	x	x	x	x	x	x	X	x	x	x	X	x	x	X	x	x	x
Deep Phenotyping Participants (n=160)																	
Biospecimen					x			x									
RNA PAXgene																x	
Blood Serum																	
Whole Blood																	
Neuroimaging- fMRI				x				x								x	
Conditioned Pain Modulation (CPM) Test					x				x								x
Cuff Ascending and Pseudorandom					x				x								x
Multimodal Automated Sensory Test (MAST) and Cuff Familiarization					x				x								x
Multimodal Automated Sensory Test (MAST) Ascending					x				x								x
Temporal Summation				x				x									x
Tonic Cuff				x				x									x
Two Point Discrimination Test (TPDT)				x				x									x
Visual task				x				x									x

Only completed for deep phenotyping (n=160) participants

* Part of the HEAL minimum data set

a Randomization will only occur if PGIC≥2

b Occurs if intervention is Physical Therapy

c Occurs if intervention is MBSR

2 Introduction

2.1 Study Rationale

According to the 2011 Institute of Medicine (IOM) report, chronic pain affects more Americans than coronary heart disease, diabetes and cancer combined at an estimated cost of \$635B per year.¹ Low back pain (LBP) is the most common pain complaint in adults, and 70-85% of people will experience back pain at some point in their lifetime. Among people with acute LBP, between 10% and 15% will go on to develop chronic low back pain (cLBP)² and this chronicity is associated with higher costs, long term functional impairment, disability and poor quality of life. Concerns about the opioid epidemic, as well as an aging population that boosts the prevalence of cLBP,³ emphasize the critical need to advance how we conceptualize and treat cLBP.

At present there are data suggesting a variety of structural/mechanical, neural, psychological, cognitive, behavioral, social, and economic factors that contribute to cLBP. Acknowledgement of this complex set of pathogenic factors in the etiology and maintenance of cLBP is referred to as the biopsychosocial model of chronic pain. Not surprisingly, with so many potential contributors to this clinical disorder, inconsistent approaches to diagnosis and treatment has left many patients without adequate pain relief. The BACPAC initiative has chosen to address the many facets of the biopsychosocial model in a comprehensive and unbiased manner and provide an integrated translational approach to identifying both the underlying mechanisms operative in cLBP, as well as the treatments that work on those underlying mechanisms. The UM BACPAC MRC study proposed here will support the overall BACPAC initiative where a vast amount of data will be collected from each participant to better understand who responds to what treatment.

The most widely used treatment options for cLBP typically include a combination of medication and surgical procedures, with the goal of relieving pain and restoring function. Unfortunately, despite advances in pain management, medical interventions alone frequently cannot resolve cLBP, leaving many patients with a significant amount of pain and limited functioning. While medications can be modestly beneficial for some patients with chronic pain,⁴⁻⁷ behavioral interventions such as cognitive-behavioral therapy (CBT) have demonstrated similar, albeit modest, effects for reducing symptoms.^{5-8,11} It is now widely accepted that optimal management for cLBP includes treatments that address not just the biological cause, but also the role of psychosocial factors in the development and maintenance of chronic pain. Given the largely overwhelming effects of current treatments, chronic pain remains a serious public health issue and there must be a cultural transformation in how pain is understood, assessed and treated. One possible explanation for the small effect sizes seen with most of the current treatments for cLBP is that patients are not being adequately matched to appropriate interventions. We hypothesize that an Interventional Response Phenotyping study can identify individuals with different underlying mechanisms for their pain who thus respond differentially to evidence-based interventions for cLBP. To address this hypothesis, we will conduct a sequential, multiple assignment, randomized trial (SMART) for the treatment of cLBP with the following three aims:

Aim 1: To perform an Interventional Response Phenotyping study in a cohort of cLBP patients. We will perform a pragmatic trial using a cohort of cLBP patients, who will receive a sequence of interventions known to be effective in cLBP. For 4 weeks, all cLBP participants will receive a web-based behavioral self-management program for pain. After the four weeks, individuals with significant levels of pain interference will be randomized in a Sequential, Multiple Assessment, Randomized Trial (SMART) to a series of treatments, including: a) mindfulness-based stress reduction (n=110), b) physical therapy and exercise (n=110), c) acupressure self-management (n=110), or d) duloxetine (n=110). After 8 weeks, individuals who remain symptomatic will be re-randomized to a different treatment for an additional 8 weeks.

Aim 2: To demonstrate that currently available, clinically-derived measures, can predict differential responsiveness to the above therapies. We will leverage the above study to perform the most comprehensive study-to-date of currently available predictors for commonly used cLBP therapies. All patients enrolled in Aim 1 will complete baseline clinical phenotyping that will include the following potential predictors of treatment response: a) demographics, b) questionnaires assessing underlying pain mechanisms, c) ambulatory symptom

monitoring, d) extensive psychological assessment using validated patient-reported outcomes, e) structured physical examination, and f) state-of-the-art structural imaging of the back and pelvis.

Aim 3: To identify new experimental measures that predict differential responsiveness to each of the above therapies, as well as to infer mechanisms of action of treatments. A subset of individuals (n=160) from the larger cohort in Aims 1 and 2 will be asked to participate in an expanded phenotyping study that will include structural and functional brain neuroimaging, quantitative sensory testing (QST), plasma measures of inflammation, and digital measurement of autonomic tone.

